6.5.1.5. Choice of chest physiotherapy treatment

The clinical physiotherapist will define the chest physiotherapy treatment modalities according to the formulated clinical hypothesis. The following treatments may be proposed :

- No chest physiotherapy treatment indicated;
- Refer to the intensivist;
- Non-invasive ventilation;
- CPAP (if non-ventilated patient) or PEEP modifications (if ventilated patient);
- Manual or ventilator hyperinflation;
- Mechanical in-exsufflator (Cough Assist ©);
- Rib cage compressions, manual assisted cough;
- Endo or naso-tracheal suctioning;
- Positioning;

- Semirecumbent position (head 45° from bed);
- Laterocubitus;
- Early mobilization:
 - Sitting on side of bed;
 - Standing;
 - Sitting on chair.

The choice of treatment according to the clinical hypothesis is defined in annexe 2b. The clinical physiotherapist will define the chest physiotherapy treatment modalities for the primary clinical hypothesis. The chest physiotherapy treatment modalities will be defined both before and again separately after the LUS and Diaphragm US examination.

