7.4.5. LUS reporting to clinical physiotherapist and intensivist

The clinical physiotherapist and intensivist reviews the LUS report. Taking into account these LUS report, the clinical physiotherapist once again selects the chest physiotherapy treatment modalities indicated. The second chest physiotherapy treatment modalities will be recorded, with the reasons for a change of interventions (if indicated). The intensivist will again review any medical decisions that have been made. The new medical treatment for hypoxemia (or cause of hypoxemia) is recorded.

7.4.6. Second visit of the clinician physiotherapist: implementation of the chest physiotherapy treatment

After the review of the LUS report, the clinical physiotherapist may or may not decide to perform the chest physiotherapy treatment, to refer the patient to the intensivist, dependent upon his/her therapeutic strategy choice. The executed chest physiotherapy treatment provided will be recorded. The following data will be recorded:

- Current medical management:
 - o Oxygen therapy (and flow);
 - o Mechanical ventilation, NIV (PEEP, IPAP);
- Severity score: SOFA
- Vital signs: RR, HR, BP SpO₂, FiO₂ (true or estimated), body temperature, RASS, Glasgow coma score;
- Adverse effects during the chest physiotherapy treatment:
 - o Desaturation (< 4% of initial SpO₂);
 - o Decrease or increase of blood pressure (> 20% of initial SBP or DBP);
 - o Decrease or increase of heart rate (> 20% of initial heart rate);
 - o Endotracheal tube removal;
 - o Catheter or perfusion removal.

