7.4.8. Patient follow-up synthesis

	Pre-inclusion J 0	Inclusion J 0	First clinical physiotherapist visit J 0	LUS J 0	LUS results reading by the clinical physiotherapist and intensivist J 0	Second clinical physiotherapist visit J 0	End- research visit
Information consent	✓						
Demographic data		✓					
Reason for hospitalization, medical diagnosis if different		✓					
Medical management			✓			✓	
SAPSOFA , vital signs			✓			✓	
Medical diagnostic for respiratory condition		✓					
Medical treatment planned for respiratory condition		✓					
Clinical hypotheses of the clinical physiotherapist			✓		✓		
Choice of chest physiotherapy protocol			✓		✓		
LUS scan				✓			
LUS-scan report				✓	✓		
New choice of chest physiotherapy protocol						✓	
Adverse effect recording						✓	
New medical treatment planned for hypoxemia					✓		
ICU length of stay, duration of MV, vital status							✓

The data will then be entered in an e-CRF (Redcap.com) and analysed at the St. Joseph Hospital Network.

The statistical analysis will be conducted by the Clinical Research Centre (CRC) of the St. Joseph Hospital Network. An identifier will be attributed to each patient (initials of first name and family name – year of birth) and the data will be entered on an EXCEL file, which will be sent to the statistician in charge of the analysis at the St. Joseph Hospital Network.

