Lung and diaphragm US is a diagnostic tool used in routine practice in ICUs by predominantly physicians. It has been validated as a tool to screen for pulmonary consolidation, atelectasis, interstitial syndrome, pleural effusion, pneumothorax and diaphragm dysfunction (16,30). The sensitivity and specificity of LUS are greater than those for chest X-ray at diagnosing these diseases in patients hospitalized in ICUs who present signs of acute respiratory failure (hypoxemia). LUS is non-invasive, painless and does not involve radiation. There are no contra-indications and no adverse side effects. We expect that LUS findings may lead to a modification in decisions concerning chest physiotherapy by both the physiotherapist and the physicians. The choice of the chest physiotherapy and medical treatment protocol are made by the physiotherapist and physician, respectively, in charge of the patient and is based on the clinical assessments and clinical parameters available and according to the benefit/risk ratio. Usually, the availability of these elements varies depends on the clinical situation and physiotherapist and physician establish their treatment plan or may decide not to intervene if treatment is not indicated or could have increased patient risk. The addition of a lung and diaphragm US will not modify this choice based on the patient's

safety. Moreover, the chest physiotherapy techniques and medical treatment used are those conventionally used.

10. Expected benefits for patients

We expect that decisions for chest physiotherapy may be modified when the physiotherapist and intensivist have access to the results of lung and diaphragm US as well as the usual clinical and imaging parameters.

The sensitivity and specificity of LUS is greater than that for the tools usually used by intensivists and physiotherapists (auscultation, chest X-ray, clinical examination) to explore respiratory dysfunction and to determine indications for chest physiotherapy. LUS may affect the management of patients with regard to chest physiotherapy by providing a more precise evaluation of the respiratory status and should lead to a more appropriate chest physiotherapy treatment.

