The expected benefit for patients is therefore that they will be given a chest physiotherapy protocol that is better suited to the type of respiratory dysfunction. This may include more optimal physiotherapy techniques for the patient, the decision not to intervene if physiotherapy is not indicated and more effective referral to the ICU physician in cases of doubt or suspicion of a condition that may warrant physician intervention.

If the results of this investigation are positive, we plan to conduct another randomised controlled trial, with patients allocated to chest physiotherapy guided by lung ultrasound or clinical examination alone, with the objective to evaluate the impact of the use of LUS on respiratory function, time on mechanical ventilation, mortality rates and hospital length of stay).

11. Risks for patients taking part in the study

No additional treatment or diagnostic studies are administered as part of this study. The lung and diaphragm US will be performed via the trans-thoracic approach. The examination is therefore non-invasive, completely painless and requires no exposure to radiation.

13. Funding

This study will be funded by the CHU de Dijon, the Forcilles' hospital and the Paris St Joseph Hospital Network for the French centre and by the University of Technology Sydney for the Australian centre. Funding will cover the time spent by the physiotherapist doing the LUS-scans, the time spent by the clinical research technician to collect the data, and by the CRA to monitor the study and take part in the statistical analysis.

14. Data recording in the Case Report Form

All of the data will be recorded in an e-CRF (<https://projectredcap.org>) and will be available for each investigator. All data will be anonymised.

15. Ethical and regulatory aspects

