PSL: Parasternal line; AAL: Anterior axillary line; PAL: Posterior axillary line

Scanning procedure

[figure not shown]
Interstitial syndrome: Investigation is performed at the anterior and lateral thoracic areas. A positive region is defined by the presence of three or more B-lines in a longitudinal plane between two ribs, and a positive exam suggests the presence of two or more positive regions. A convex probe is used.

Consolidation: Examination begins with the lung area of interest (refer to clinical assessment) and may involve the entire lung if necessary. A convex probe is used.

Pneumothorax: In the supine patient, the sonographic technique consists of exploration of the least gravitationally dependent areas progressing laterally. A convex or a linear probe may be used.

Pleural effusion: In the supine patient, the ultrasound probe is placed in the postero-inferior area in the transverse view. The maximum distance between the parietal and visceral pleura (PLD) is measured 3 cm above the inferior pole of the lung at the end of expiration.

Diaphragm assessment – excursion and thickness *(If ventilated patient use PSV mode with PS = 7 and PEEP = 0)*

Diaphragm excursion: Anterior subcostal approach: the probe is placed between the anterior axillary line and the mid-clavicular line. B-mode is initially used to determine the best approach and select the exploration line. After the diaphragm is identified, excursion measurements are performed in M-mode: the diaphragm moves toward the probe during inspiration and away from it during expiration. The distance between the end-inspiration and end-expiration points defines the diaphragm excursion. A diaphragm excursion < 2.5 cm (Lerolle Chest, 2009) indicates a diaphragm dysfunction.

Diaphragm thickening: the probe is placed in an intercostal space between the mid-axillary line and the anterior axillary line, 0.5 cm to 2 cm below the costo-diaphragmatic sinus. In B-mode, the diaphragm is observed as a structure made of three distinct layers: a non-echogenic central layer bordered by two echogenic layers. The diaphragm thickening fraction (DTF) measurement is obtained in B-mode using the following formula: $DTF (\%) = [(end-inspiration\ thickness - end-expiration\ thickness) / (end-expiration\ thickness) \times 100]$. A DTF < 25% indicates a diaphragm dysfunction.

Annexe 3b: LUS Semiology

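### Annexe 3a calls for PSV with PS = 7 and PEEP = 0 during the diaphragm scan in ventilated, hypoxemic patients; section 11 does not mention this, and the plan gives transient events during the scan no place to be recorded

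*Combined protocol and SAP*

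**What the plan says.** Annexe 3a gives, in parentheses beside the title of the diaphragm assessment, the ventilator condition for excursion and thickness: "If ventilated patient use PSV mode with PS = 7 and PEEP = 0". It states no exemption, tolerance criterion, duration or return to previous settings, and does not say who makes the change.

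Section 11 sets out the risks: "No additional treatment or diagnostic studies are administered as part of this study". It describes a trans-thoracic scan and concludes: "The examination is therefore non-invasive, completely painless and requires no exposure to radiation". Section 9 says of lung and diaphragm ultrasound in general: "There are no contra-indications and no adverse side effects".

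Section 6.5.1.5 includes among the chest physiotherapy options "CPAP (if non-ventilated patient) or PEEP modifications (if ventilated patient").

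Section 7.4.6, the second physiotherapist visit, introduces its safety list as "Adverse effects during the chest physiotherapy treatment". The first item reads "Desaturation (< 4% of initial" SpO2). In the 7.4.8 schedule the row "Adverse effect recording" has a single tick, at that visit.

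**The concern.** The protocol specifies a ventilator mode and pressures for a measurement made in patients who are all hypoxemic. It also treats PEEP as therapy: 6.5.1.5 lists its modification as a treatment, and Annexe 2b assigns PEEP to intubated patients with pneumonia, lobar obstructive atelectasis or pleural effusion. Setting PEEP to zero for a measurement is therefore a study procedure that the risk section would be expected to mention.

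Two things are at stake. The visible risk text is incomplete for ventilated patients. And if a patient desaturates briefly, or has a short change in blood pressure or heart rate, while on the specified setting, the case report form as described has no item for it. The study could then report no scan-related events only because none were collected.

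**Working it through.** No statistical formula applies and the plan gives no figure to reproduce. The check compares the sections and counts entries.

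**Who is exposed.** Sections 5.1 and 6.4 require SpO2/FiO2 < 315. Ventilated patients are in the study: 6.5.1.5 and Annexe 2b give them treatments, and 7.4.3 records their settings.

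**When.** The scan (7.4.4) follows the first physiotherapist visit (7.4.3). The report is then read (7.4.5), and the second physiotherapist visit (7.4.6) comes after that. At that visit chest physiotherapy may or may not be given.

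**What is recorded at each step** (7.4.3 to 7.4.8 and Annexe 4):

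| Item | First physiotherapist visit | Ultrasound | Results reading | Second physiotherapist visit |
|---|---|---|---|---|
| Vital signs | yes | no | no | yes |
| Ventilator settings | yes | yes (Annexe 4) | no | yes |
| Adverse effects | no | no | no | yes, worded for chest physiotherapy |

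**Counts.**
- 7.4.6 has 5 adverse-effect items: desaturation, blood pressure, heart rate, endotracheal tube removal, and catheter or perfusion removal. None is assigned to the ultrasound visit.
- 7.4.8 has 7 columns. Adverse effects are ticked in 1 and vital signs in 2.
- The ultrasound column has 2 ticks, for the scan and its report. Neither is a safety item.
- Section 7.2 names 4 hospitals, 3 of them French. Section 6.5.2.2 places a referent intensivist at scans done by a French physiotherapist. None is stated for the remaining 4 − 3 = 1 site.

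**Following three kinds of event through the record.**
1. *A transient fall in SpO2 that recovers before the second visit.* Vital signs may look unchanged at both visits, and Annexe 4 shows the settings but has no event field. Nothing is recorded.
2. *A lasting change in vital signs.* It can appear at the second visit, but nothing ties it to the scan.
3. *PEEP not restored.* Comparing settings before, at and after the scan would show it.

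Only the first is missed outright. The second is captured without attribution, and the third is traceable.

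**Patients who get no chest physiotherapy.** The 7.4.8 tick is not conditional on treatment, whereas the 7.4.6 wording is, so their coverage is unclear. On either reading the scan itself is not covered.

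**The desaturation item.** Read literally, a change of less than 4% counts as an event. The neighbouring blood pressure and heart rate items use > 20%. The inequality is reversed and should be corrected before the list is used a second time.

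**The case against.** The strongest reply is that the record already brackets the scan. Vital signs, a severity score and ventilator settings are taken at both physiotherapist visits, and Annexe 4 records settings at the scan. When a French physiotherapist scans, a referent intensivist attends and validates the report, and an intensivist reviews the report under 7.4.5. This stands, and it confines the gap to transient events and to attribution. It does not close the gap: the referent intensivist's stated role is to check that the scan is properly done, and Annexe 4 has no field for tolerance.

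Several stronger readings are tempting, and the documents do not support them.
- *Every ventilated patient is switched to these settings.* Annexe 4 offers other modes (ACV, SIMV, PCV, NIV), and some patients may already be on PSV or on low PEEP. The instruction has no exemption, but how often a change occurs is not stated.
- *Patients are not told.* The information sheets (Annexes 5a and 5b) and the text between 6.1 and 6.4 were not available. The point is limited to the visible risk text.
- *Section 11's statement that nothing additional is given is plainly false.* A measurement condition is not a therapy merely because PEEP modification appears among the treatments, and whether this setting is routine at these sites cannot be judged from the documents. What can be said is that section 11 is silent on it.
- *Section 9 is contradicted.* Its sentence is a general statement about ultrasound as a tool, and the point does not depend on it.

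**Conclusion.** The point holds in limited form. A protocol-specified ventilator setting for hypoxemic patients is missing from section 11, and adverse effects are collected only for chest physiotherapy at a later visit. The consequence is that transient events during the scan go unrecorded and lasting ones are not attributed to it.

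Its size cannot be expressed in patients or events. The documents give no ventilated share, no prior PEEP and no event rate, and the schedule counts above describe coverage, not risk. A reader might infer that the primary result is biased or that harm is likely. Neither follows: the primary criterion uses diagnostic agreement and treatment modification, which this gap does not touch, and nothing in the documents quantifies the hazard.

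The conclusion assumes that Annexe 3a is followed as written in at least some patients not already on these settings, and that no unseen form collects events at the scan. It is worth correcting because the remedy is small.

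**What to change.** 1. Add to section 11 that ventilated patients not already on these settings are placed on PSV with PS = 7 and PEEP = 0 for the diaphragm scan, and that their previous settings are restored afterwards. Restoration would be a new step, since the protocol states neither a duration nor a return to prior settings.
2. Record the 7.4.6 adverse-effect items at the ultrasound visit (7.4.4), with a tick in that column of 7.4.8, whether or not chest physiotherapy follows. The bedside treating team should complete them, or the referent intensivist where present. The operator should not, being blinded to the patient's status. Nor should the clinical physiotherapist: having that person at the scan would threaten the operator's blinding and the before-and-after comparison, which relies on findings arriving through the written report.
3. Reword the desaturation item as a fall of more than 4% from initial SpO2.

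Qualifying the section 9 sentence, and stating whether the Annexe 4 settings block refers to the lung or the diaphragm part, are optional. No alternative ventilator setting is proposed here.

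The cost is a sentence or two in section 11, one existing form block used twice, one corrected item, and slightly more data entry for staff already at the bedside. At the Australian site, where no referent intensivist is stated, the entry falls to the treating team.
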